4.1. Protocol Deviations

Important protocol deviations (including deviations related to study inclusion/exclusion criteria, conduct of the trial, patient management or patient assessment) will be summarized.

Protocol deviations will be tracked by the study team throughout the conduct of the study.

These protocol deviations will be reviewed to identify those considered as important as follows:

CONFIDENTIAL

Statistical Analysis Plan 213051

- Data will be reviewed prior to freezing the database to ensure all important deviations are captured and categorized in the protocol deviations SDTM dataset.
- This dataset will be the basis for the summaries of important protocol deviations.

A separate listing of all inclusion/exclusion criteria deviations will also be provided. This listing will be based on data as recorded on the inclusion/exclusion page of the eCRF.

To facilitate presenting protocol deviations that occurred due to the COVID-19 pandemic, the description of protocol deviations occurring because of COVID-19 will include the standard text “COVID-19” as per the Data Management guidance issued on “COVID-19 Designation of protocol deviations”.

After a discussion with the study team, the following analyses will be included:

[1] Protocol deviations that occurred due to the COVID-19 pandemic

[2] List which subjects were impacted due to the COVID-19 pandemic and how their participation was impacted

[3] Summarize the number of missed visits due to the COVID-19 pandemic

[4] Summarize the number of missed assessments for key endpoints due to the COVID-19 pandemic (if not fully described based on the summary of missed visits)

[5] Summarize the number of visits where assessments were performed using alternative methods due to the COVID-19 pandemic.

5. STATISTICAL ANALYSES

5.1. General Considerations

5.1.1. General Methodology

Confidence intervals will use 95% confidence levels unless otherwise specified.

Summary tables (except for Safety and PK analyses) will provide the following descriptive

statistics:

- Continuous data (normal data): n, mean, standard deviation (SD), median, interquartile range, minimum and maximum.

- Continuous data (log normal data): n, geometric mean, standard deviation (SD) on the log

scale, and between subject variability(%CVb)

- Categorical data: number and percentage of participants in each category.

CONFIDENTIAL

Statistical Analysis Plan 213051

5.1.2. Baseline Definition

For all endpoints the baseline value will be the latest pre-dose assessment in each treatment period (Prior to the oral dose) in each treatment period), with a non-missing value, including those from unscheduled visits. If time is not collected, Day 1 assessments are assumed to be taken prior to first dose and used as baseline. For subjects who did not receive study treatment during the study, baseline will be defined as the latest, non-missing collected value. Day 1 pre-dose ECGs for each treatment period will be performed in triplicate. In such case of triplicate measurement for pre-dose average will be used as baseline.

Unless otherwise stated, if baseline data is missing no derivation will be performed and baseline will be set to missing.

5.2. Primary Endpoint(s) Analyses

The PK analyses will be based on the pharmacokinetic analysis set.

The plasma pharmacokinetic concentrations will have different nomenclatures dependent on the method of measuring. For measured concentrations of GSK3640254 in plasma, the nomenclature [¹⁴C]-GSK3640254 describes the parent GSK3640254 concentration derived via analysis by liquid chromatography (LC) + Accelerator Mass Spectrometry (AMS), whereas GSK3640254 describes the parent GSK3640254 concentration derived via liquid chromatography-tandem mass spectrometry (LC-MS/MS). It is expected that, for period 1, the radiolabelled iv dose will be measured using LC+AMS and will be labelled “[¹⁴C]-GSK3640254”, the non-radiolabelled oral dose will be measured using LC-MS/MS and will be labelled “GSK3640254”. For period 2, the radiolabelled oral dose will be measured using LC-MS/MS and will be labelled “GSK3640254”. For the reporting of displays a footnote will be added to detail the nomenclature used to discriminate between labelled and non-labelled drug (and the analytical methods used to provide the data).

Total radioactivity measurements in urine samples and faecal homogenates will be determined by Liquid Scintillation Counting (LSC) and/or by AMS. Total radioactivity measurements from plasma derived from blood will be analysed, as appropriate, by AMS in Treatment Period 1 and by LSC and/or by AMS, for Treatment Period 2, as detailed in the SRM.

The reconciliation of the Plasma PK Case Report Form (CRF) and SMS2000 data will be provided by DM(GSK) and the analytical CROs – Pharmaron, and Covance will also perform reconciliation and provided via their analytical reports.

Derivation of plasma pharmacokinetic parameters for [¹⁴C]- GSK3640254, total radioactivity and GSK3640254 will be performed by, or under the direct auspices of, Clinical Pharmacology Modelling and Simulation (CPMS), GlaxoSmithKline.

Derivation of urine/faeces total radioactivity parameters will be performed by the analytical CROs – Pharmaron, and Covance via their analytical reports.

CONFIDENTIAL

Statistical Analysis Plan 213051

5.2.1. Definition of endpoint(s)

- AUC(0-inf), AUC(0-t), C_{max}, t_{max} and t_{1/2} of parent and total drug-related material (radioactivity) in plasma.
- Volume of distribution at steady-state (V_{ss}) and clearance (CL) of parent after IV dose (Period 1 only)
- Renal clearance of parent (CL_r) after IV and oral administration
- Oral Clearance (CL/F) and apparent volume of distribution (V_z/F) for the parent following oral administration
- Direct evaluation of absolute bioavailability (F), indirect calculation of fraction of drug escaping first pass hepatic clearance (F_h), fraction absorbed (F_a) and fraction of drug escaping gut metabolism (F_g)
- Urinary and fecal cumulative excretion of total radioactivity as a percentage of the total radioactive dose (Period 1 and Period 2)

5.2.1.1. Drug concentration measures

Refer to the Output and Programming Specification (OPS) document for Data Display Standards & Handling Conventions for Pharmacokinetic Data.

Plasma GSK3640254, [¹⁴C]- GSK3640254 and blood and Plasma total radioactivity concentration-time data will be listed for each participant and standard summary statistics will be calculated (i.e. arithmetic mean, standard deviation, median, minimum and maximum) by treatment and planned sampling time.

Individual participant, mean and median plasma GSK3640254, [¹⁴C]- GSK3640254 and total radioactivity concentration-time profiles will be plotted for each treatment on both a linear and semi-log scale.

For urine and feces, the total radioactivity excreted in urine and feces per sample or collection interval will be listed by subject. The cumulative total and the cumulative percentage of the total radioactive dose will be calculated and listed by subject. The concentration of radioactivity in urine, feces and fecal homogenates will be expressed as ng equivalents/g.

5.2.1.2. Derived Pharmacokinetic Parameters**5.2.1.2.1. Derived plasma pharmacokinetic parameters**

PK Parameters will be calculated by standard non-compartmental analysis according to current working practices and using the currently supported version of WinNonlin version 6.3 or above. All calculations of non-compartmental parameters will be based on actual sampling times. PK parameters listed will be determined from plasma GSK3640254, [¹⁴C]-GSK3640254, total radioactivity as data permits and unless otherwise stated.

Table 4 Derived Pharmacokinetic Plasma Parameters

Parameter	Parameter Description
AUC(0-t)	Area under the concentration-time curve from time zero to the time of the last quantifiable concentration (C(t)) will be calculated using the linear trapezoidal rule for each incremental trapezoid and the log trapezoidal rule for each decremental trapezoid.
λ_z	The first order rate constant associated with the terminal (log-linear) portion of the concentration-time curve.
AUC(0- ∞)	Area under the concentration-time curve extrapolated to infinity will be calculated as: $AUC(0 - \infty) = AUC(0 - t) + \frac{C(t)}{\lambda_z}$
%AUCex	The percentage of AUC (0- ∞) obtained by extrapolation (%AUCex) will be calculated as: $\frac{[AUC(0 - \infty) - AUC(0 - t)]}{AUC(0 - \infty)} * 100$
Cmax	Maximum observed concentration, determined directly from the concentration-time data.
tmax	Time to reach Cmax, determined directly from the concentration-time data.
t _{1/2}	Apparent terminal half-life will be calculated as: $t_{1/2} = \ln 2 / \lambda_z$
CL	Total clearance calculated as: $CL = \frac{Dose(IV)}{AUC(0 - \infty)}$ Treatment Period 1, analyte [¹⁴ C]-GSK3640254 only and where the Dose(IV) is the actual IV dose provided by Covance, Harrogate
Vss	Volume of distribution at steady-state, calculated as:

Parameter	Parameter Description
	$V_{ss} = CL * MRT_{iv}$ 
Where CL is total clearance and MRT is the mean residence time, calculated as AUMC(0-∞) [Area under the first moment curve]/AUC(0-∞)

CLr	
If plasma AUC(0-∞) is calculable, then
 $CLr = \frac{\text{Cumulative Ae[Urine] for Period 1}}{\text{Plasma AUC}(0 - \infty)}$ 
If plasma AUC(0-∞) is not calculable, then
 $CLr = \frac{\text{Cumulative Ae[Urine] for Period 1}}{\text{Plasma AUC}(0 - t)}$ 
Where cumulative urine Ae from excretion data for treatment Period 1 and AUC from NCA PK analysis of Treatment Period 1, analyte [¹⁴C]-GSK3640254 only

ML(iv)	
Metabolite load following intravenous administration, calculated as:
 $ML(iv) = \frac{[\text{Total Radioactivity AUC}(0 - \infty) - [^{14}\text{C}]GSK3640254 \text{ AUC}(0 - \infty)]}{\text{Total Radioactivity AUC}(0 - \infty)}$ 
Treatment Period 1

ML(po)	
Metabolite load following oral administration, calculated as:
 $ML(po) = \frac{[\text{Total Radioactivity AUC}(0 - \infty) - GSK3640254 \text{ AUC}(0 - \infty)]}{\text{Total Radioactivity AUC}(0 - \infty)}$ 
Treatment Period 2
 
Note: GSK3640254 AUC(0-∞) may be updated depending on the sample analysis conducted but refers to the parent GSK3640254 from oral dose

Fg	
Fraction metabolized by gut wall as a fraction of the oral dose, calculated as:
 $Fg = 1 - [ML(po) - ML(iv)]$

CONFIDENTIAL

Statistical Analysis Plan 213051

Parameter	Parameter Description
$CL_{h,iv,blood}$	
Hepatic blood clearance, calculated as:
 $CL_{h,iv,blood} = CL_{h,iv,plasma} * \text{blood to plasma ratio}$ 
Where $CL_{h,iv,plasma}$ is the hepatic plasma clearance calculated as:
 $CL_{h,iv,plasma} = CL - CL_r$
E_h	
Hepatic extraction ratio, calculated as:
 $E_H = CL_{h,iv,blood} / Q_h$ 
Where Q_h = hepatic blood flow (literature value of 1660 mL/min, Edginton, 2006)
 
Note: if assumption that hepatic CL accounts for 100% of the clearance (i.e. CL_r is negligible), then $E_h = CL * \text{blood to plasma ratio} * Q_h$

F_h	$F_h = 1 - E_h$
F_a	
Fraction absorbed following an oral dose, calculated as follows
 $F_a = \frac{F(0 - \infty)] / (1 - E_H)}{F_g}$
Dose(iv)	Radiometric IV dose calculated by Covance
Dose(oral)	Radiometric oral dose calculated by Covance
$F(0-\infty)$	
Oral absolute bioavailability based on $AUC(0-\infty)$, calculated as:
 $F(0 - \infty) = \frac{GSK3640254 \text{ AUC}(0 - \infty)(\text{oral})}{\text{Dose}(\text{oral}) \frac{\text{Dose}(\text{iv})}{[14C]GSK3640254 \text{ AUC}(0 - \infty)(\text{iv})}}$ 
Per Subject

CONFIDENTIAL

Statistical Analysis Plan 213051

Parameter	Parameter Description
	Note: Radiometric dose will be used for IV. GSK3640254 AUC(0-∞) (Oral) refers to the parent GSK3640254 from oral dose, but may be updated depending on the sample analysis
F(0-t)	
Oral absolute bioavailability based on AUC(0-t), calculated as:
 $F(0-t) = \frac{\text{GSK3640254 AUC}(0-t)(\text{oral})}{\frac{\text{Dose}(\text{oral})}{\text{Dose}(\text{iv})} * \frac{[14C]\text{GSK3640254 AUC}(0-t)(\text{iv})}{[14C]\text{GSK3640254 AUC}(0-t)(\text{iv})}}$ 
Per Subject
 
Note: Radiometric dose will be used for IV. GSK3640254 AUC(0-t) (Oral) refers to the parent GSK3640254 from oral dose, but may be updated depending on the sample analysis

CL/F	
Apparent oral clearance, calculated as:
 $CL/F = \frac{\text{Dose}}{AUC(0-\infty)}$
Vz/F	
Apparent volume of distribution based on the terminal phase
 $Vz/F = \frac{\text{Dose}}{[\lambda_z * AUC(0-\infty)]}$
GSK3640254/ Total radioactivity ratio for Cmax	
Cmax Ratio = Exp {[log_e(GSK3640254 Cmax)] - [log_e(Total radioactivity Cmax)]}
 
Per subject for radiolabelled oral dose. GSK3640254 may be updated depending on the sample analysis conducted but refers to the parent GSK3640254 from oral dose

GSK3640254/ Total radioactivity ratio for AUC(0-∞)	
Cmax Ratio = Exp {[log_e(GSK3640254 AUC(0-∞))] - [log_e(Total radioactivity AUC(0-∞))]}
 
Per subject for radiolabelled oral dose. GSK3640254 may be updated depending on the sample analysis conducted but refers to the parent GSK3640254 from oral dose

GSK3640254/ Total radioactivity	
Cmax Ratio = Exp {[log_e(GSK3640254 AUC(0-t))] - [log_e(Total radioactivity AUC(0-t))]}

CONFIDENTIAL

Statistical Analysis Plan 213051

Parameter	Parameter Description
ratio for AUC(0-t)	Per subject for radiolabelled oral dose. GSK3640254 may be updated depending on the sample analysis conducted but refers to the parent GSK3640254 from oral dose
[¹⁴ C]-GSK3640254/ Total radioactivity ratio for Cmax	Cmax Ratio = $\text{Exp} \{[\log_e([\sup{14}\text{C}]\text{-GSK3640254 Cmax}) - [\log_e(\text{Total radioactivity Cmax})]]\}$ Per subject for radiolabelled IV dose
[¹⁴ C]-GSK3640254/ Total radioactivity ratio for AUC(0-∞)	Cmax Ratio = $\text{Exp} \{[\log_e([\sup{14}\text{C}]\text{-GSK3640254 AUC}(0-\infty)) - [\log_e(\text{Total radioactivity AUC}(0-\infty))]]\}$ Per subject for radiolabelled IV dose
[¹⁴ C]-GSK3640254/ Total radioactivity ratio for AUC(0-t)	Cmax Ratio = $\text{Exp} \{[\log_e([\sup{14}\text{C}]\text{-GSK3640254 AUC}(0-t)) - [\log_e(\text{Total radioactivity AUC}(0-t))]]\}$ Per subject for radiolabelled IV dose

Notes:

- Additional parameters may be included as required
- Lambda_z is the terminal phase rate constant
- The following PK parameters AUC(0-∞), AUC(0-t), %AUC_{ex}, Cmax, t_{max}, t_{1/2}, CL, V_{dss}, V_z/F and CL/F, will be derived in Phoenix and sent to S&P. The radiometric IV and oral doses will be calculated by Covance and sent to S&P. Additional parameters will be derived by S&P including CL_r, ML(iv), ML(po), F_g, E_h, F_h Fa, F(0-∞), F(0-t) and the [¹⁴C]-GSK3640254/total radioactivity ratios.

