3. OBJECTIVES AND ENDPOINTS

Objectives	Endpoints
Primary	

 To determine parent GSK3640254 and total drug-related radioactivity systemic concentrations following a single IV microtracer dose of [14C]-GSK3640254 (with an oral dose of non-radiolabelled GSK3640254) and oral dose of [14C]-GSK3640254¹ 	
 AUC(0–inf), AUC(0–t), Cmax, tmax and t1/2 of parent and total drug-related material (radioactivity) in plasma and blood. Volume of distribution at steady state (Vss) and clearance (CL) of parent after IV dose (Period 1 only). Renal clearance of parent (CLr) after both IV and oral dose Oral clearance (CL/F) and apparent volume of distribution (Vz/F) for the parent following oral administration

 To calculate the absolute oral bioavailability of GSK3640254 	
 Direct estimation of absolute oral bioavailability (F), indirect calculation of fraction of drug escaping first pass hepatic clearance (Fh), fraction absorbed (Fa) and fraction of drug escaping gut metabolism (Fg)

 To determine the rate and extent of excretion of total radioactivity in urine and feces and the total recovery of radioactivity, following IV and oral administration of [14C]-GSK3640254 	
 Urinary and fecal cumulative excretion as a percentage of the total radioactive dose
Secondary	

 To evaluate the safety and tolerability of GSK3640254 after single IV and oral doses in healthy participants. 	
 Characterize observed adverse events, and abnormal laboratory, 12-lead ECG, and vital signs assessments observed.

 To determine the blood:plasma ratio of [14C]-GSK3640254-related materials (total radioactivity) associated with blood cellular components 	
 Blood:plasma ratio of [14C]-GSK3640254-related materials (total radioactivity)

Exploratory	

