4. STUDY DESIGN

4.1. Overall Design

This is a single group, single center, [¹⁴C]-GSK3640254 mass balance study with a two-period, single sequence, and no masking.

This open-label, single-center, non-randomised, 2-period, single-sequence, mass balance study will enroll a cohort of 6 healthy male participants. The aim of the study is to assess the pharmacokinetics, balance/excretion, and metabolism of GSK3640254 using [¹⁴C]-radiolabelled drug substance administered as an IV infusion of a microtracer dose with an oral tablet, non-radiolabelled dose (Treatment period 1) and a [¹⁴C]-radiolabelled drug substance administered orally (Treatment Period 2).

Four to six healthy participants are deemed sufficient. To minimise the number of exposed to radiation, participants who discontinue early will not be replaced unless the total number of participants who complete dosing and all critical assessments drops below 4.

Each participant will be involved in the study for up to 10 weeks. He will have a screening visit, two treatment periods (Treatment Periods 1 and 2), separated by a washout period of at least 13 days between oral doses, and a follow-up visit 7 – 14 days after the last assessment in Treatment Period 2. During both treatment periods, participants will reside in the unit from the morning of Day -1 until all procedures are completed at 168 h post-dose (on Day 8). Participants may be asked to stay for up to 1 week longer in Treatment Period 2, if excretion of drug-related material takes longer than anticipated (see [Figure 1](#)).

Safety data will include AE reporting, 12-lead ECG, vital signs, and laboratory safety tests. Blood will be sampled extensively on the day of dosing and daily until Day 8, for assessing the PK of GSK3640254 and metabolites.

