4.1.1. Screening Period

Participants must be screened within 30 days before the first dose of GSK3640254 and must meet all eligibility criteria.

Treatment Period 1 (oral tablets and ¹⁴C-intravenous infusion)

On Day 1 of Treatment Period 1, after an overnight fast of at least 8 h, each participant will take a single 200 mg oral dose (2 x 100 mg tablets) of GSK3640254 with a moderate fat meal (approximately 600 calories with approximately 30% of calories from fat); the IV infusion of 100 µg of [¹⁴C]-GSK3640254 (approximately 3.7 kBq; 100 nCi) will begin 5 h after oral dose and continue over 1 h. Blood samples, all voided urine, and feces will be collected continuously from Day 1 through Day 8, while duodenal bile will be collected as described below. Participants will be discharged on study Day 8 after completion of the 168-h sample collection and other planned assessments and instructed to return to the clinic on Day -1 of Treatment Period 2.

A non-invasive device (Entero-tracker) to collect duodenal bile will be used in Treatment Period 1. The bile string will be swallowed 2 h after the oral dose and 3 h before the IV infusion starts, a duration recommended to allow transit of the string to the duodenum. Participants will fast from insertion of the bile string until the completion of the IV infusion, at which point a food cue (small standard high-fat meal) will be given to stimulate gall bladder emptying. The Entero-tracker will be removed about 1.5 h after the IV infusion stops (7.5 h after the oral dose).

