8.5.2. Urine Sample Collection

Urine samples will be collected over the time periods specified in the [SoA](#). Urine samples will be used to determine total radioactivity excreted in urine and for subsequent metabolite profiling (to be analysed under a separate protocol).

All participants will be asked to void their bladders before study intervention administration. A blank (pre-dose) urine sample will be collected pre-dose (up to 3.5 h before oral dosing) in Treatment Periods 1 and 2. After oral dosing, in each Treatment Period, urine will be collected over 24 h collection periods as follows: 0-24 h, 24-48 h, 48 – 72 h, 72 – 96 h, 96 – 120 h, 120-144 h, 144-168 h. Further details of urine sample collection, processing, storage and shipping procedures are provided in the SRM.

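### SAP Table 4 divides whole-period urine by plasma AUC over a different time window, so renal clearance is biased low by default and the summary may mix two different quantities

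*SAP*

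**What the plan says.** The CLr row of SAP Table 4 (section 5.2.1.2.1) has two branches. The first opens with "If plasma AUC(0-∞) is calculable, then" and divides cumulative Period 1 urinary recovery by AUC(0-∞). The second opens with "If plasma AUC(0-∞) is not calculable, then" and divides the same recovery by AUC(0-t). The row's note confirms that only the denominator changes: "Where cumulative urine Ae from excretion data for treatment Period 1 and AUC from NCA PK analysis of Treatment Period 1", for the [¹⁴C]-labelled parent.

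The windows are set elsewhere:

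- **Urine.** Protocol 8.5.2: "After oral dosing, in each Treatment Period, urine will be collected over 24 h collection periods as follows", with seven intervals ending at 168 h.
- **IV timing.** Protocol 4.1.1: the infusion "will begin 5 h after oral dose and continue over 1 h".
- **Plasma.** Protocol 4.1: "Blood will be sampled extensively on the day of dosing and daily until Day 8".
- **AUC(0-t).** SAP Table 4 runs it "from time zero to the time of the last quantifiable concentration", so its end point is set by each man's data.

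Protocol section 3 lists "Renal clearance of parent (CLr) after both IV and oral dose" under the first primary objective, and SAP 5.2.2 has it summarised and listed. Table 4 computes the percentage of AUC extrapolated but sets no limit on it, and it does not say when AUC(0-∞) counts as calculable. Nothing in the supplied text cuts the urine at the last quantifiable plasma time or asks for a partial AUC to the end of urine collection.

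**The concern.** Renal clearance is the amount excreted over an interval divided by the plasma AUC over that same interval. The default branch never meets that condition, because the urine stops at 168 h and the AUC does not. The fallback meets it only when the last quantifiable plasma sample coincides with the end of urine collection.

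The two branches therefore estimate different quantities. If both are used in one study, the mean and the between-subject spread of CLr depend partly on whose AUC(0-∞) was judged calculable. That judgement has no written rule and would be made with the data in view, in 4 to 6 men. At stake is the accuracy and comparability of the reported CLr values.

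This is separate from the question of what is measured in urine. Table 5 defines Ae[urine] as total radioactivity, while SAP 5.4.1.1 says unchanged drug will be used for renal clearance. Those two need reconciling, but settling the analyte would not align the windows.

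**Working it through.** The plan states no CLr value to reproduce. The check is the size of the window error, assuming that parent is measured in urine.

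**Inputs from the documents.** Urine ends 168 h after the tablet. The IV starts at 5 h and lasts 1 h. Urine therefore covers T = 168 − 5 = 163 h from the start of the IV. The first 5 h contain no labelled drug from this dose.

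**Assumed.** Constant renal clearance, one-compartment decline, and half-lives of 24, 48 and 72 h. Times of last quantifiable plasma concentration (tlast) are also assumed; the Period 1 sampling table is not in the supplied text.

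**Formulas.** With constant renal clearance, Ae(0-T) = CLr × AUC(0-T). Let f(T) = AUC(0-T)/AUC(0-∞), with times from the start of the IV. For a 1 h infusion and k = ln 2 / half-life,

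f(T) = 1 − [exp(−k(T−1)) − exp(−kT)]/k.

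Then, as estimated CLr divided by true CLr:

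- default branch: f(163), always below 1;
- fallback: f(163)/f(tlast − 5), with tlast counted from the tablet. It equals 1 if tlast is 168 h and exceeds 1 if tlast is earlier.

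**Worked case, half-life 48 h.** k = 0.01444. f(163) = 0.904, so the default is low by 9.6%. For tlast 120 h, f(115) = 0.809 and the fallback is 0.904/0.809 = 1.118.

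| Half-life | Default | Fallback, tlast 168 h | tlast 144 h | tlast 120 h |
|---|---|---|---|---|
| 24 h | 0.991 | 1.000 | 1.009 | 1.029 |
| 48 h | 0.904 | 1.000 | 1.046 | 1.118 |
| 72 h | 0.791 | 1.000 | 1.074 | 1.184 |

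At a half-life of 12 h the default is 0.9999, so the error vanishes.

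**Sensitivity to model shape.** If the terminal phase carries only part of the AUC, the default error shrinks in proportion. At 48 h, a share of 60% gives 1 − 0.6 × 0.0957 = 0.943, and 30% gives 0.971.

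**Effect on a mixed summary.** Take six men with identical true CLr, two of them on the fallback. The ratio between the two kinds of value is 1/f(tlast − 5). Call its log d. The log-scale variance created by mixing is d² × (4 × 2/6)/5.

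- Half-life 24 h: tlast 168 h gives a ratio of 1.009 and an artefactual CV of 0.5%; tlast 120 h gives 1.038 and 1.9%.
- Half-life 48 h: tlast 168 h gives 1.106 and 5.2%; tlast 120 h gives 1.237 and 11.0%.

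In the last case the geometric mean is exp[(4 ln 0.904 + 2 ln 1.118)/6] = 0.97 of the truth. The errors partly cancel in the mean and appear as spread.

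**With matched windows** the ratio is 1.00 for any half-life and any tlast under the same assumption.

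**The case against.** The strongest reply is that much of this is contingent. Blood sampling nominally runs to Day 8, as urine does. If the final sample is quantifiable, the fallback is exactly matched. Mixing needs AUC(0-∞) to fail in some men but not all. Both points stand.

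A reader might infer that the CLr summary will contain values biased in opposite directions, with men of equal CLr differing 1.6-fold. The documents do not support that. The figure needs a 48 h half-life with tlast at 72 h. With daily samples, plasma would then stand at 39% of its end-of-infusion value at 72 h and 27% at 96 h. The assay limit would have to lie between about 0.8 and 1.2 ng/mL against a projected peak of about 3 ng/mL (Protocol 4.3). Nothing suggests so high a limit for an AMS assay chosen for a microtracer. Even the 120 h example at 48 h implies a limit of roughly 0.4 to 0.6 ng/mL (14% to 19% of 3), so it is illustrative only.

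Nor do the documents show that the fallback applies mainly to short profiles. AUC(0-∞) can also fail because decline is too slow to define by Day 8. Then tlast is the final sample and the fallback is the correct branch.

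A reader might also infer serious damage to hepatic clearance and the parameters built on it. SAP Table 4 itself allows for negligible CLr, and the only excretion data are 0.04% urinary (Protocol Appendix 6; rats, oral dose, so transfer to IV dosing in man is an assumption). If CLr were 1% of CL, a 21% error in it would move CL − CLr by 0.21% of CL.

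Finally, CLr is descriptive and the SAP's estimand table labels it supplementary. Individual values are listed, and PK handling conventions are deferred to a programming document not supplied. These lower the stakes, but none of the supplied text aligns the windows. The default branch is low whatever tlast is.

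**Conclusion.** The point holds as a defect in a stated formula, of modest and uncertain size. The default CLr is biased low by construction: under 1% at a half-life of 24 h or less, about 10% at 48 h and 21% at 72 h, and less if the terminal phase carries only part of the AUC. The fallback is correct when tlast is 168 h and high otherwise, by about 3% (24 h) or 12% (48 h) for tlast 120 h. Whether the two will be mixed cannot be told from the documents, since calculable is undefined and neither half-life nor assay limit is given.

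The conclusion rests on constant renal clearance, parent being the urine analyte, and the assumed half-lives and tlast values. It concerns the reported CLr, an endpoint under the first primary objective. The consequence for CL − CLr, Eh, Fh and Fa is probably negligible if urinary excretion is low. The SAP should be corrected because the error is avoidable at little cost.

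**What to change.** Replace both branches in the CLr row of Table 4 with CLr = Ae(0-τ)/AUC(0-τ), using the same τ in numerator and denominator for each participant, and delete the AUC(0-∞)/AUC(0-t) switch. Let τ be the end of the last urine interval that ends at or before the last quantifiable plasma time. State the clock: with τ counted from the tablet, the IV partial AUC runs from the start of the infusion to τ − 5 h after it. Choose τ on nominal times, so that a final sample drawn minutes early does not discard a whole urine interval. List τ beside each CLr value.

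Confirm first how parent in urine will be quantified. Urine is collected in 24 h intervals, but SAP 5.4.1.1 takes unchanged drug from a separate metabolism report and does not say whether it is measured by interval or in pools. If only pooled samples are available, use the partial AUC over the pool's window.

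The cost is SAP wording and one extra partial-AUC output, with no new samples. The downside is that urine collected after τ is not used for CLr; it remains in the excretion tables.
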